3.2. Visit 1: Screening and Dose Escalation Period (Day -20 to Day 1)

Reminders

- Once consented and eligibility is confirmed, subjects with fluctuations and prescribed levodopa should take their daily levodopa dose so that they are in an ON state when the MDS-UPDRS is administered. For most subjects, this would be approximately 60 minutes after taking levodopa.
- Subjects must have discontinued and refrain from using any laxatives, constipation medications, and other medications as specified in [Section 7](#) for 14 days prior to starting ENT-01 dosing. (These “washout” days are not counted in the schedule, as described below.)

Perform the assessments and procedures as listed in Appendix 2: Schedule of Events:

- Informed consent
- Inclusion/Exclusion Criteria
- Demographics/Medical History
- Complete Physical Exam
- Weight (Height from ENT-01-030 will be used, so it is not required to be recorded)
- Orthostatic Vital Signs: Vital signs will include supine blood pressure and heart rate, sitting or standing blood pressure and heart rate, respiratory rate, and body temperature. Supine measurements will be taken after the subject has been in the supine position for at least 5 minutes. Sitting or standing measurements will be taken within 5 minutes of the subject sitting or standing from the supine position.
- 12-lead EKG
- Labs (chemistry, hematology, and urinalysis): as defined in [Appendix 1: Laboratory Tests](#).
- Pregnancy Testing – For women of child-bearing potential, this is done on-site with the urine pregnancy kit (UPT) provided. If the on-site UPT is positive, then a serum pregnancy test will be done. For post-menopausal women less than 60 years of age, a serum FSH will be done at the screening visit only.
- Instruct subject to refrain from using or discontinue the use of any laxatives, constipation medications, and other medications as specified in [Section 7](#) for 14 days prior to starting ENT-01 dosing. Determine the date ENT-01 dosing should begin and provide to the subject. (Although Visit 1 is listed as Day -20, that is more of a rough estimate for schedule planning. Most subjects should get to their fixed dose before 20 days; at that point Day 1 for that subject is set and their remaining visits are scheduled based on Day 1.)

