A Phase 2a study involving 50 patients with Parkinson's disease and constipation was recently conducted (RASMET; IND 130770, NCT03047629). The purpose of the study was to assess the safety, tolerability, pharmacokinetics, and pharmacodynamics of orally administered medication to relieve symptoms of constipation associated with Parkinson's disease. The study consisted of an 8 to 12-week Stage 1 period, and an 8 to 10-week Stage 2 period. All subjects received the study drug during one of the observational periods of the study. The study evaluated the safety of ENT-01, and its effect on bowel function and neurologic symptoms.

In Stage 1, 10 patients received escalating single doses from 25 to 200 mg/day or maximum tolerated dose (MTD). The goal was to determine safety and tolerability. In Stage 2, 34 patients received daily doses escalating from 75 to a maximum of 250mg/day, a dose that induced change in bowel function or MTD, followed by a "fixed" dose for 7 days, and a 2-week washout. Primary efficacy endpoint was defined as increase of 1 complete spontaneous bowel movement (CSBM)/week, or 3 CSBM/week over 14-day baseline period. Safety was also assessed.

In Stage 2, 82.4% patients achieved the primary efficacy endpoint. Mean CSBM/week increased from 1.2 at baseline to 3.6 during fixed dose ($p=1.2\times10^{-7}$) (Hauser et al., 2019). Common adverse events included nausea in 21/44 (47%) and diarrhea in 18/44 (40%) patients. No study-drug related serious adverse events were reported. The only SAE was a GI bleed after medication was discontinued in one patient. This patient was on aspirin, Plavix, and Motrin, and the SAE was considered unrelated to study medication. There were no deaths. The only other noteworthy AE was dizziness 8/44 (18%). Dizziness was graded as moderate in one patient who was receiving an alpha-adrenergic blocking agent (Terazosin). This patient was withdrawn from the study and recovered spontaneously. All other AEs resolved spontaneously without discontinuation of ENT-01. The details of the RASMET study AEs are in the study report contained in IND 130770.

Significant and lasting improvements were observed in total MDS-UPDRS scores ($p=0.0008$), the MDS-UPDRS-Part III scores (motor component) ($p=0.0006$), cognition (MMSE) ($p=0.0004$), hallucinations, sleep, and circadian rhythm ($p=0.016$). Hallucinations improved in 5/6 patients. Systemic absorption was $< 0.3\%$.

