3.3. Visit 2: Beginning of Fixed Dose Period (Day 1, +3 days)

This visit is to be done within 3 days from dose fixing. Perform the assessments and procedures as listed in [Appendix 2: Schedule of Events](#):

- Brief Physical Exam (review of body systems as indicated)
- Weight
- Orthostatic Vital Signs: Vital signs will include supine blood pressure and heart rate, sitting or standing blood pressure and heart rate, respiratory rate, and body temperature. Supine measurements will be taken after the subject has been in the supine position for at least 5 minutes. Sitting or standing measurements will be taken within 5 minutes of the subject sitting or standing from the supine position.
- 12-lead EKG
- Labs (chemistry, hematology, urinalysis, pregnancy): as defined in [Appendix 1: Laboratory Tests](#).
- IP Collection and Accountability
- Dispense Rescue Medication, as needed. Subjects continue appropriate use of rescue medication, ensuring adequate bowel movements every 3 days.
- Dispense ENT-01 for 6 weeks of dosing with instructions regarding dosing.
- Re-educate subject with respect to stool diary daily entries.
- Assess for Adverse Events (new, ongoing, since last visit, etc.)
- Review Concomitant Medications/Therapies (current, since last visit, etc.)
- MDS-UPDRS – Only Parts I, II, and III of the scale will be rated, assessed by personnel certified in the MDS-UPDRS. Subjects with fluctuations and prescribed levodopa should be assessed when in an ON state. Non-fluctuating subjects and subjects not on levodopa can be assessed at any point during the visit.
- SAPS-PD (for subjects who scored > 0 on the SAPS-PD at screening.)

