10.3. CTCAE Definitions of Dose Limiting Adverse Events

Table 2: NCI CTCAE v. 4.03 Definitions for DLT Adverse Events

Adverse Event	Grade 1	Grade 2	Grade 3	Grade 4	Grade 5
Diarrhea (watery stool)	Increase of <4 stools a day over baseline	Increase of 4-6 stools a day over baseline	Increase of >7 stools a day; incontinence; hospitalization indicated	Life threatening complications: urgent intervention indicated	Death
Vomiting	1-2 episodes per 24 hours	3-5 episodes per 24 hours	6 or more episodes in 24 hours; tube feeding, TPN or hospitalization indicated	Life-threatening consequences: urgent intervention indicated	Death
Postural hypotension ³	Mild, transient lightheadedness or dizziness upon rising from lying or sitting position that does not interfere with ADL	Moderate lightheadedness, dizziness or fainting upon rising from lying or sitting position that limits instrumental ADL; Non-urgent medical intervention indicated	Severe lightheadedness, dizziness or fainting upon rising from lying or sitting position that limits self-care ADL; Medical intervention or hospitalization indicated	Life-threatening and urgent intervention indicated	Death

³Definition adapted from combining CTCAE definitions for Hypotension and Dizziness

10.4. Criteria for Dose Limiting Toxicity (DLT) Endpoints:

- Recurrent vomiting: 3-5 episodes of vomiting within 24 hours of taking study medication (Grade 2 adverse event)
- Recurrent diarrhea: >7 episodes of diarrhea within 24 hours of taking study medication (Grade 3 adverse event)
- Dizziness: Moderate lightheadedness or fainting upon rising from lying to sitting or standing and severe enough to require medical intervention within 24 hours of taking study medication (Grade 2 adverse event) or either a systolic blood pressure less than 80mmHg or diastolic blood pressure less than 40mm Hg.

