10.15. Stopping Rules

It is anticipated that no more than 2 subjects out of 50 (4.0 %) will have an AE of Grade 4 or Grade 5 that is at least possibly related to ENT-01 in this Study. Should there be more than 2 subjects with an AE grade 4 or 5 that is at least possibly related to ENT-01 in the cohort of subjects, the study will be put on an immediate clinical hold. Safety Monitoring processes are identified in [Section 10.14](#).

In addition, individual safety stopping criteria will include:

- Reaching DLT before a prokinetic effect
- Serious Adverse Event at least possibly attributable to ENT-01.
- Having a non-DLT gastrointestinal adverse event > grade 3 within 24 hours of taking ENT-01 that is at least possibly attributable to ENT-01
- A fall in systolic blood pressure to < 80 mm Hg upon rising from lying to sitting or standing
- A fall in diastolic blood pressure to < 40 mm Hg upon rising from lying to sitting or standing

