11.3. Safety Analyses

All safety analyses will be performed on the Safety Population. The safety data will be presented in individual listings and summary tables.

Adverse Events

AEs will be coded according to the latest version of the Medical Dictionary for Regulatory Activities (MedDRA). The intensity/severity of AEs will be graded according to NCI-CTCAE v.4.03.

TEAEs, AEs leading to study treatment discontinuation, AEs leading to dose interruption, AEs related to study medication, SAEs, and AEs leading to death will be summarized by system organ class, preferred term, and study period (Screening, dose escalation, Fixed Dose, Wash-Out). A summary of AEs that are CTCAE Grade 3 or higher, as well as the most frequent preferred terms, will be provided.

If a subject experiences the same preferred term multiple times within a period, then the event will be counted only once within the period and by greatest severity.

Descriptive statistics will be used to summarize the safety data both by treatment group and overall.

Clinical Laboratory Values

All laboratory test results will be summarized by period together with the change from baseline. The frequency distribution for low/normal/high or normal/abnormal will be summarized as well. The denominators for calculating the percentages will be based on the number of subjects with non-missing values in the Safety Population.

Vital Signs

Vital sign results will be summarized by period, together with the change from baseline.

Physical Examination

Summaries of physical examinations will present frequency distribution of abnormal findings by body system and period. The denominators for calculating the percentages will be based on the number of subjects evaluated for a particular body system of each dose level in the Safety Population.

Electrocardiogram (EKG)

EKG findings will be classified as normal vs abnormal. The number and percentage of each category will be summarized using frequency table for each period. The denominators for calculating the percentages will be based on the number of subjects with non-missing values in each period.

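### Upright blood pressure and heart rate may be taken sitting or standing, at any time within 5 minutes of rising, so their change from baseline can reflect posture or timing instead of drug

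*Combined protocol and SAP*

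**What the plan says.** Sections 3.2 to 3.6 describe orthostatic vital signs in the same words at every visit: "Vital signs will include supine blood pressure and heart rate, sitting or standing blood pressure and heart rate, respiratory rate, and body temperature". The supine reading is standardised: "Supine measurements will be taken after the subject has been in the supine position for at least 5 minutes". The upright reading is not: "Sitting or standing measurements will be taken within 5 minutes of the subject sitting or standing from the supine position". No section ties a subject's posture, or the time after rising, to what was used at an earlier visit.

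Section 2.1 names vital signs among the safety endpoints of the primary objective. Section 11.3 gives their analysis in one sentence: "Vital sign results will be summarized by period, together with the change from baseline". It does not mention posture, does not define a supine-to-upright difference, and does not say which reading is the vital-sign baseline. Under Section 3.1, a subject who rolls over within 14 days of the last ENT-01-030 visit need not repeat procedures common to both studies, so some Visit 1 readings may come from the parent trial.

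Two other sections set blood pressure limits. In 10.4 the dizziness criterion can also be met by "either a systolic blood pressure less than 80mmHg or diastolic blood pressure less than 40mm Hg", with no posture or time attached to the reading. In 10.15 the individual stopping criteria include "A fall in systolic blood pressure to < 80 mm Hg upon rising from lying to sitting or standing" and "A fall in diastolic blood pressure to < 40 mm Hg upon rising from lying to sitting or standing". These accept either posture and give no time.

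**The concern.** The upright reading is there to detect an orthostatic effect, and it is the one part of the vital-sign procedure left open. If a subject is measured sitting at Visit 1 and standing at Visit 4, and standing pressure is the lower, the record shows a fall that the drug did not cause. In the reverse order, a real fall can be hidden. A later or earlier reading within the 5 minutes can act in the same way.

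The design makes this harder to see. There is one arm, so no control group carries the same artefact. About 50 subjects are spread over up to 20 sites (Section 3), an average of 50 / 20 = 2.5 per site. If posture and time are not recorded, no later analysis can recover them.

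**Working it through.** **Plan's own figure.** The plan gives no figure on this point. Its one sample-size figure (11.7) reproduces, 1 - 0.95^50 = 0.923 against the stated 92%, but nothing below depends on it.

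**Inputs.** From the protocol: either posture, a window of 0 to 5 minutes, five visits, and about 40 completers (Section 4). Not in the protocol, so assumed: the sitting-standing gap *d*, the share of subjects who switch posture, and the SD of change.

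**One subject, no true change.** Assume systolic values of 130 supine, 120 sitting and 105 standing at both visits. The subject sits at Visit 1 and stands at Visit 4.

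- Supine change: 130 - 130 = 0 mmHg.
- Upright change: 105 - 120 = -15 mmHg; in the reverse order, +15 mmHg.
- Supine-to-upright difference: 120 - 130 = -10 at Visit 1 and 105 - 130 = -25 at Visit 4, a change of -15 mmHg.

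So the upright reading and the supine-to-upright difference carry the whole artefact, and the supine reading carries none.

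**Mean change.** Size of bias = net one-way switch rate × *d*. With an assumed net rate of 20% (0.20 × 40 = 8 of the completers):

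| Assumed gap *d* (mmHg) | Bias in mean change (mmHg) |
|---|---|
| 5 | 0.20 × 5 = 1 |
| 15 | 0.20 × 15 = 3 |
| 30 | 0.20 × 30 = 6 |

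If equal numbers switch each way, the net rate is zero and so is the bias.

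**Noise under balanced switching.** Assume that posture is a 50/50 choice at each visit, independent of everything else, and that the SD of change is 12 mmHg with posture held constant. Then SD = √(12² + 2 × 0.5 × 0.5 × *d*²):

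- *d* = 5: √(144 + 12.5) = 12.5 mmHg
- *d* = 10: √(144 + 50) = 13.9 mmHg
- *d* = 15: √(144 + 112.5) = 16.0 mmHg

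**Absolute limits.** These are not changes from baseline, so switching between visits cannot create a false change in them. How often they are met does depend on posture. Assume a sitting systolic with mean 110 and SD 15, normally distributed. The chance of a reading below 80 is Φ((80 - 110)/15) = Φ(-2) = 2.3% sitting. With standing pressure lower by 5, 10 or 15 mmHg it is Φ(-1.67) = 4.8%, Φ(-1.33) = 9.1% or Φ(-1) = 15.9%. This shows only that posture matters to these limits; the inputs are not from the protocol.

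**The case against.** The strongest reply is that little is shown to go wrong. Posture switching is permitted, not planned, and pooling of sitting with standing readings is inferred from the silence of 11.3. Section 11.2 leaves detail to a separate SAP and 13.12 mentions eCRF completion guidelines; neither is in the document reviewed, and either could call for posture to be recorded. Switching with no net direction leaves the mean unbiased. All of this stands, and it limits the size of the point. It does not remove it: a site that follows 3.2 to 3.6 exactly may still collect non-comparable upright readings, and an SAP cannot restore a posture or time that was not held constant or recorded.

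A reader might also infer more than the protocol supports:

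- **That vital-sign change from baseline is unreliable as a whole.** It is not. The supine readings have a fixed posture and a minimum rest, and respiratory rate and temperature are not at issue.
- **That the dose-limiting and stopping criteria are undermined.** The limits are absolute, and 10.15 expressly accepts either posture. No section ties these limits to the scheduled visit readings. Dosing starts at home after Visit 1 and no visit is scheduled until the dose is fixed (3.2, 3.3). The dizziness criterion is mainly symptom-based; Section 2.1 gives it no blood pressure limb. What remains is that 10.4 and 10.15 describe the qualifying reading differently.
- **That the 18% dizziness rate in the Phase 2a study (8/44, Section 1) measures what is at risk.** It counts all reported dizziness. Section 1 describes one patient with moderate dizziness, 1/44 = 2.3%, and the criterion in 2.1 starts at Grade 2.
- **That the mean is biased by 3 mmHg.** This needs 20% of subjects to switch in one direction with a 15 mmHg gap. Neither value is in the protocol.

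**Conclusion.** The point holds for the upright readings and for the supine-to-upright difference. The text at all five visits allows different postures and times for one subject, and 11.3 summarises change from baseline without separating them. An apparent change, or the absence of one, could then be due to posture or timing.

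The size cannot be found from the protocol. Under the assumptions stated, it runs from no bias and some added noise (balanced switching) to 1 to 6 mmHg in the mean (20% net one-way switching, gap 5 to 30 mmHg). The direction for a subject who switches rests on standing pressure being lower than sitting. This is a weakness in one component of the primary safety data that is cheap to remove. It is not evidence that the safety conclusions will be wrong.

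**What to change.** 1. **Sections 3.2 to 3.6:** require the same upright posture and the same fixed time after rising for each subject at every visit. Apply this also where the Visit 1 reading is carried over from ENT-01-030 under 3.1, so that later readings match it.
2. **eCRF:** record the posture and the time after rising with each upright reading.
3. **Section 11.3:** summarise the supine-to-upright difference and its change from Visit 1, with sitting and standing subjects shown separately.
4. **Sections 10.4 and 10.15:** reconcile them on the posture and timing of the readings to which their blood pressure limits apply. No view is given here on the limits or on which posture they should use. Prescribing one posture for all subjects could change how often an individual stopping criterion is met, so that choice belongs to this reconciliation and not to a measurement clarification.

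The cost is one sentence per visit description, one or two eCRF fields, one table, and slightly less flexibility for sites. No extra visit, staff or equipment is needed.

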The dose will be taken upon awakening on an empty stomach along with 8 oz. of water. Subjects prescribed levodopa should wait at least 30 minutes between taking levodopa and study medication. The subject will be instructed to not eat for at least 60 minutes after study drug administration. Tea, coffee with/without milk/sugar and orange juice (without pulp) are permitted. Plain yoghurt can be added if the patient experiences repeated nausea. Dosing will be increased every 2-3 days until a pro-kinetic dose or the maximum dose is reached. If the subject has not

produced a CSBM within 24 hours on at least 4 of 5 consecutive days, then they will increase their daily dose by 1 tablet (by 25 mg). This incremental dosing will continue until the subject:

- reaches the prokinetic dose (the dose producing a CSBM within 24 hours on at least 4 of 5 consecutive days). The subject then remains on that dose until Visit 4;
- reaches the maximum dose of 10 tablets (250mg for active treatment); or,
- reaches the dose limiting tolerability (DLT).

If the subject has 7 or more discrete episodes of diarrhea separated by 30 minutes or more within 24 hours at any dose on 2 consecutive days, the dose will be reduced by 25mg and fixed at that dose (assuming the diarrhea abates at the lower dose).

Should a prokinetic response not occur at the maximum allowed number of tablets (10 tablets or 250mg), subjects will continue to take 10 tablets throughout the Fixed Dose period.

Site staff will review subject diary entries daily and contact subjects as needed to ensure subject safety, compliance with study and dosing instructions, and to determine the subject's individual fixed dose level. The day that a subject "fixes" their dose for the first time (as determined by site staff) is considered Day 1 for the purposes of scheduling subsequent study visits.

3.3. Visit 2: Beginning of Fixed Dose Period (Day 1, +3 days)

This visit is to be done within 3 days from dose fixing. Perform the assessments and procedures as listed in [Appendix 2: Schedule of Events](#):

- Brief Physical Exam (review of body systems as indicated)
- Weight
- Orthostatic Vital Signs: Vital signs will include supine blood pressure and heart rate, sitting or standing blood pressure and heart rate, respiratory rate, and body temperature. Supine measurements will be taken after the subject has been in the supine position for at least 5 minutes. Sitting or standing measurements will be taken within 5 minutes of the subject sitting or standing from the supine position.
- 12-lead EKG
- Labs (chemistry, hematology, urinalysis, pregnancy): as defined in [Appendix 1: Laboratory Tests](#).
- IP Collection and Accountability
- Dispense Rescue Medication, as needed. Subjects continue appropriate use of rescue medication, ensuring adequate bowel movements every 3 days.
- Dispense ENT-01 for 6 weeks of dosing with instructions regarding dosing.
- Re-educate subject with respect to stool diary daily entries.
- Assess for Adverse Events (new, ongoing, since last visit, etc.)
- Review Concomitant Medications/Therapies (current, since last visit, etc.)
- MDS-UPDRS – Only Parts I, II, and III of the scale will be rated, assessed by personnel certified in the MDS-UPDRS. Subjects with fluctuations and prescribed levodopa should be assessed when in an ON state. Non-fluctuating subjects and subjects not on levodopa can be assessed at any point during the visit.
- SAPS-PD (for subjects who scored > 0 on the SAPS-PD at screening.)

3.4. Visit 3: 6th week of FDP (Day 43, +/- 3 days)

Perform the assessments and procedures as listed in [Appendix 2: Schedule of Events](#):

- Brief Physical Exam (review of body systems as indicated)
- Weight
- Orthostatic Vital Signs: Vital signs will include supine blood pressure and heart rate, sitting or standing blood pressure and heart rate, respiratory rate, and body temperature. Supine measurements will be taken after the subject has been in the supine position for at least 5 minutes. Sitting or standing measurements will be taken within 5 minutes of the subject sitting or standing from the supine position.
- 12-lead EKG
- Labs (chemistry, hematology, urinalysis, pregnancy): as defined in [Appendix 1: Laboratory Tests](#).
- IP Collection and Accountability
- Dispense Rescue Medication, as needed. Subjects continue appropriate use of rescue medication, ensuring adequate bowel movements every 3 days.
- Dispense ENT-01 for 6 weeks of dosing with instructions regarding dosing.
- Re-educate subject with respect to stool diary daily entries.
- Assess for Adverse Events (new, ongoing, since last visit, etc.)
- Review Concomitant Medications/Therapies (current, since last visit, etc.)
- MDS-UPDRS – Only Parts I, II, and III of the scale will be rated, assessed by personnel certified in the MDS-UPDRS. Subjects with fluctuations and prescribed levodopa should be assessed when in an ON state. Non-fluctuating subjects and subjects not on levodopa can be assessed at any point during the visit.
- SAPS-PD (subjects who scored > 0 on the SAPS-PD at screening)

3.5. Visit 4: 12th week of FDP, Start of WOP, ET (Day 85, +/- 3 days)

Perform the assessments and procedures as listed in [Appendix 2: Schedule of Events](#):

- Brief Physical Exam (review of body systems as indicated)
- Weight
- Orthostatic Vital Signs: Vital signs will include supine blood pressure and heart rate, sitting or standing blood pressure and heart rate, respiratory rate, and body temperature. Supine measurements will be taken after the subject has been in the supine position for at least 5 minutes. Sitting or standing measurements will be taken within 5 minutes of the subject sitting or standing from the supine position.
- 12-lead EKG
- Labs (chemistry, hematology, urinalysis, pregnancy): as defined in [Appendix 1: Laboratory Tests](#).
- IP Collection and Accountability
- Reinstate all discontinued medications, antacids, proton pump inhibitors and laxatives.
- Dispense Rescue Medication, as needed. Subjects continue appropriate use of rescue medication, ensuring adequate bowel movements every 3 days.
- Re-educate subject with respect to stool diary daily entries.
- Assess for Adverse Events (new, ongoing, since last visit, etc.)
- Review Concomitant Medications/Therapies (current, since last visit, etc.)
- MDS-UPDRS – Only Parts I, II, and III of the scale will be rated, assessed by personnel certified in the MDS-UPDRS. Subjects with fluctuations and prescribed levodopa should be assessed when in an ON state. Non-fluctuating subjects and subjects not on levodopa can be assessed at any point during the visit.
- SAPS-PD (for subjects who scored > 0 on the SAPS-PD at screening.)
- MMSE

3.6. Visit 5: End of 6-week Wash-out Period/End of study (Day 127, +/- 3 days)

Perform the assessments and procedures as listed in [Appendix 2: Schedule of Events](#):

- Brief Physical Exam (review of body systems as indicated)
- Weight
- Orthostatic Vital Signs: Vital signs will include supine blood pressure and heart rate, sitting or standing blood pressure and heart rate, respiratory rate, and body temperature. Supine measurements will be taken after the subject has been in the supine position for at least 5 minutes. Sitting or standing measurements will be taken within 5 minutes of the subject sitting or standing from the supine position.
- 12-lead EKG
- Labs (chemistry, hematology, urinalysis, pregnancy): as defined in [Appendix 1: Laboratory Tests](#).
- Assess for Adverse Events (new, ongoing, since last visit, etc.)
- Review Concomitant Medications/Therapies (current, since last visit, etc.)
- MDS-UPDRS – Only Parts I, II, and III of the scale will be rated, assessed by personnel certified in the MDS-UPDRS. Subjects with fluctuations and prescribed levodopa should be assessed when in an ON state. Non-fluctuating subjects and subjects not on levodopa can be assessed at any point during the visit.
- SAPS-PD (for subjects who scored > 0 on the SAPS-PD at screening.)
- Collect eDiary device.

